#### ***Mortality primary outcomes***

*Mortality primary outcome 1:* mortality in 1-59 month olds, assessed at 2.5 years (based on at most 2 years of follow-up per community), comparing the 1-59 month and the placebo arms. Assuming a standard deviation of approximately 0.023, we find that 1,116 communities per arm will provide approximately 80% power to detect a 10% relative reduction, assuming a baseline mortality rate of 27 per thousand person-years among children 1-59 months old and an alpha of 0.05. The absolute effect size is a mortality rate difference of 2.7 deaths per 1000 person-years. This calculation is based on the standard Z-test formula for power (treating the mortality rate in each community as a continuous variable). The calculation does not involve a correction for multiple comparisons since the analysis uses a hierarchical testing approach for the three mortality outcomes, as described below.

*Mortality primary outcome 2:* mortality in 1-11 month olds, assessed at 2.5 years (based on at most 2 years of follow-up per community), comparing the 1-11 month arm and the placebo arm. Assuming a standard deviation of approximately 0.074, we find that 1,116 communities per arm will provide approximately 80% power to detect a 19% relative reduction, assuming a baseline

mortality rate of 45 deaths per thousand person-years among children 1-11 months old and an alpha of 0.05. The absolute effect size is a mortality rate difference of 8.8 per 1000 person-years. This calculation is based on the standard Z-test formula for power (treating the mortality rate in each community as a continuous variable). The calculation does not involve a correction for multiple comparisons since the analysis uses a hierarchical testing approach for the three mortality outcomes, as described below.

*Mortality primary outcome 3:* mortality in 12-59 month olds, assessed at 2.5 years (based on at most 2 years of follow-up per community), comparing the 1-11 month and 1-59 treatment arms. Assuming a standard deviation of approximately 0.022, we find that 1,116 communities per arm will provide approximately 80% power to detect a 11% relative reduction, assuming a baseline mortality rate of 24 deaths per thousand person-years among children 12-59 months old and an alpha of 0.05. This corresponds to an absolute reduction of 2.7 in the death rate per 1000 person-years. This calculation is based on the standard Z-test formula for power (treating the mortality rate in each community as a continuous variable).

Sensitivity analyses for primary outcomes based on reduced enrollment caused by security or logistical concerns: if only the first half of Tahoua communities are enrolled by 2.5 years, with 791 communities per arm, we anticipate the following detectable relative detectable effect sizes (respectively): 12%, 23% and 13%, for 1-59 months, 1-11 months and 12-59 months.

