1.3. Revisions History

Date	Version	Edit
13-5-20	2	Fixed adding error in Table 2 to reflect the correct grappe interval primary outcomes total of 12,300, Section 4
19-5-20	2	Added [name] as additional US-based Medical Monitor, Section 1
26-5-20	2	Added [name] to list of study personnel in title page
29-5-20	2	Added UCSF IRB study number to title page
29-5-20	2	Updated mortality numbers to reflect most recent IHME data, Section 4.2
24-6-20	2	Removed [name] from list of Investigators and Study Personnel in title page
30-Jun-20	2	Updated study design schematic, Section 4 (Figure 1)
30-Jun-20	2	Updated sentence to indicate that AMR communities are included in the primary mortality outcome in the Mortality Trial, Section 4.5
30-Jun-20	2	Add sentence about addition of parallel implementation trial with arm description and rationale sentence, Section 4.1
1-Jul-20	3	Revised CRISP in list of collaborators, Section 1
2-Jul-20	4	Added detail about implementation trial, Sections 1.2, 3, 4.1, 4.4.2, 4.4.8, 4.5, 4.6, 4.10
2-Jul-20	4	Updated formatting of table of contents
15-Jul-20	5	Added detail about implementation trial, Sections 1.2, 3, 4.1, 4.4.2, 4.4.8, 4.5, 4.6, 4.10
31-Jul-20	6	Updated detail about implementation trial, Sections 1.2, 3, 4.1, 4.4.2, 4.4.8, 4.5, 4.6, 4.10 and updated formatting
3-Aug-20	7	Reordered outcomes to reflect hierarchical testing order, updated header and page numbers, added [name] to list of investigators, added CSI and CRISP to list of partnering organizations, Section 6, added interim analysis to study timeline, Section 4.6
10-Aug-20	8	Updated list of appendices to include implementation trial procedures, Section 7
12-Aug-20	9	Updated rollout table to include population numbers for all grappes. Section 4.6
16-Sept-20	10	Updated design to reflect DSMC feedback: - Increased number of communities selected for Mortality Trial to 3,000, Section 4 - Delayed start of remainder of communities until 1.5 years after the first enrollment (aligned with interim analysis), Section 4.6 - Simplified the comparison of Delivery Trial approaches to a 2-arm trial and removed mortality as an outcome, Section 4.5
05-Oct-20	11	Updated with costing/cost-effectiveness protocol changes, Sections 4.10 and 6.10
09-Oct-20	11	Updated References Section to be consistent in formatting
09-Oct-20	11	Added IRB numbers to the Executive Summary, Section 1.1

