MORDOR I demonstrated that community-level biannual distribution of oral azithromycin to children 1–59 months of age reduced mortality by nearly 14% compared to placebo over 2 years in Malawi, Niger, and Tanzania.⁴ The greatest effect was found in Niger, where communities receiving azithromycin experienced an 18% reduction in mortality compared to those receiving placebo.⁴ Subgroup analyses suggested that the youngest children might benefit the most, with reductions of approximately 23% in children 1–11 months old.⁴ In Niger, azithromycin distributions were associated with an increase in antimicrobial resistance (AMR) to macrolides after 2 years,⁵ though azithromycin remained similarly effective in reducing mortality after 3 years in MORDOR II.⁶

The World Health Organization (WHO) released conditional guidelines for this intervention which include targeting azithromycin distributions to children 1–11 months of age in high mortality settings.⁷ The rationale for targeting this age group is that the youngest children experience the highest risk of mortality and limiting distributions to the youngest children could minimize selection for antimicrobial resistance. However, distributing azithromycin to children 1–11 months alone remains untested, since MORDOR I treated children 1–59 months of age. A crude examination of relative mortality reductions by age group suggests a stronger effect in the younger age groups, but MORDOR was unable to demonstrate a differential effect by age group statistically ($P = 0.20$ for test of interaction of treatment and age).⁴ Moreover, a herd effect could have contributed to the apparent larger effect sizes in the younger groups; treating children 12–59 months may protect children 1–11 months by reducing their exposure to infectious diseases causing mortality. Finally, beyond a possible differential effect by age group, in MORDOR I–Niger there were 5 times as many children aged 12–59 months as children 1–11 months, resulting in nearly twice as many deaths averted in the older age group.⁸ The greatest societal gains may thus come from intervening on a population with a broader risk spectrum instead of targeting only the highest risk subgroups.⁹ More evidence is needed to determine the difference and magnitude of the benefit of targeting different age groups, and of the risk of inducing AMR when distributing to different age groups.

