### 3.2.4. Statistical framework

The overall analysis is divided into two aspects: 1) A single frequentist analysis, conducted at the time 2.5 years after enrollment, will test the hypothesis that azithromycin MDA reduces childhood mortality. The hypothesis tests will be superiority tests (as opposed to equivalence or noninferiority analyses) and will be two-sided. 2) Ongoing analyses beyond the primary endpoint, reflecting the perpetual nature of the trial, will be conducted using a Bayesian perspective.

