## 3.3. Statistical Principles

### 3.3.1. Confidence intervals and *P*-values

The primary analysis for the mortality trial is prespecified to occur at alpha of 0.05, as follows. We propose to use a fixed-sequence, hierarchical testing approach for the three mortality primary outcomes [4]:

The staged testing approach will maximize the trial's power. Our rationale for a fixed-sequence testing approach is if there is no benefit of treating all children 1-59 mo compared with

placebo, then the trial would be unlikely to demonstrate benefit between treatment in the narrower age subgroups. Note that the hypothesis testing in the mortality trial and implementation trial will proceed independently for primary outcomes along the same sequence of tests. Regardless of the hypothesis testing results, we will report 95% confidence intervals around estimates of the incidence rate ratio for the comparisons of the trial arms.

In the mortality trial AMR substudy, we propose a second set of tests. There are two primary outcomes measured among children 1-59 months: prevalence of macrolide resistance measured in NP swabs, and load of genetic determinants of macrolide resistance measured in rectal swabs. Each primary outcome in the substudy will be examined separately at alpha of 0.05. For each outcome, we propose three pair-wise comparisons between the study groups (Placebo v 1-59mo, Placebo v 1-11mo, 1-59mo v 1-11mo). We will compute *P*-values using a permutation test with a step-down minP approach to account for multiple testing [5,6]. Additional secondary comparisons between groups in the substudy will include prevalence of genetic determinants of resistance to non-macrolide antibiotics (NP swabs) and load of genetic determinants to non-macrolide antibiotics (rectal swabs). Within each outcome, we will report *P*-values adjusted to control the false discovery rate at 5% the Benjamini-Hochberg approach [7]. For all AMR endpoints, we will additionally report unadjusted *P*-values, which will be less conservative to detect undesirable outcomes resulting from mass distribution of azithromycin.

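### The 80% power given for mortality outcomes 2 and 3 is power if tested alone; through the fixed sequence it is lower (about 67% and 56% if each test has 80% alone)

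*SAP*

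**What the plan says.** SAP 3.2.3 treats each mortality primary outcome as a two-sample Z-test on community rates with 1,116 communities per arm. For outcome 3 (12-59 months, azithro 1-11 against azithro 1-59) it states that "1,116 communities per arm will provide approximately 80% power to detect a 11% relative reduction". Outcome 2 (1-11 months, azithro 1-11 against placebo) also gets about 80%, for a 19% reduction. On multiplicity, 3.2.3 says: "The calculation does not involve a correction for multiple comparisons since the analysis uses a hierarchical testing approach for the three mortality" outcomes.

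SAP 3.3.1 sets the level and the procedure: "The primary analysis for the mortality trial is prespecified to occur at alpha of 0.05", and "We propose to use a fixed-sequence, hierarchical testing approach for the three mortality primary outcomes". SAP 3.2.4 says that the tests are for superiority "and will be two-sided". Section 3.3.1 claims that staging the tests gives the trial its greatest power. Its reason reads: "Our rationale for a fixed-sequence testing approach is if there is no benefit of treating all children 1-59 mo compared with" placebo, then a benefit in the narrower age groups is unlikely to be shown. It also promises 95% confidence intervals whatever the tests show.

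The list or figure that should follow the colon in 3.3.1 is not shown in the text available. The order 1-2-3 is therefore inferred from the outcome numbering and from the protocol's revision log (version 7): "Reordered outcomes to reflect hierarchical testing order".

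**The concern.** A fixed sequence lets each step use the full 0.05, so leaving out an alpha correction is valid. It does not follow that each outcome keeps its stand-alone power. Outcome 2 can be claimed only if outcome 1 also succeeds, and outcome 3 only if all three do. A reader of 3.2.3 will take 80% to be the chance of a confirmatory finding for each outcome, and for outcomes 2 and 3 it is not.

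Outcome 3 is the only primary mortality comparison between the two active strategies, and it comes last. The visible rationale concerns the first gate only. The protocol (section 2) also raises a possibility that bears on the second gate: "treating children 12–59 months may protect children 1–11 months by reducing their exposure to infectious diseases causing mortality". If the earlier infant benefit came partly from treating older children, infant-only treatment could do worse on outcome 2 than planned, and outcome 3 would then often go untested.

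**Working it through.** **Inputs (SAP 3.2.3).** 1,116 communities per arm and two-sided alpha 0.05. SDs are 0.023, 0.074 and 0.022 for outcomes 1, 2 and 3. Baseline rates are 27, 45 and 24 per 1,000 person-years. Absolute effects are 2.7, 8.8 and 2.7, and relative effects 10%, 19% and 11% (that is 2.7, 8.55 and 2.64).

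**Step 1: reproduce the stated power.** SE = SD × √(2/1,116) = 0.974, 3.133 and 0.931 per 1,000. Power = Φ(effect/SE − 1.96).

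| Outcome | Effect/SE | Power alone |
|---|---|---|
| 1 (2.7) | 2.77 | 79.2% |
| 2 (8.8; 8.55) | 2.81; 2.73 | 80.2%; 77.9% |
| 3 (2.7; 2.64) | 2.90; 2.83 | 82.6%; 80.9% |

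The SAP's 80% is right as stand-alone power.

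**Step 2: correlation between the tests.** The SAP states none, but its figures imply one. Solving 27 = 45w + 24(1 − w) gives an infant share w = 3/21 = 1/7. The 5:1 ratio of older children to infants in protocol section 2 gives 1/6. With w = 1/7, the three SDs imply a between-age correlation of

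r = (0.023² − w²·0.074² − (1 − w)²·0.022²) / (2w(1 − w)·0.074·0.022) = 0.155.

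Each pair of tests shares one arm, so:

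- corr(Z1,Z2) = 0.5 × (w·0.074 + (1 − w)·r·0.022)/0.023 = 0.29
- corr(Z1,Z3) = 0.5 × ((1 − w)·0.022 + w·r·0.074)/0.023 = 0.45
- corr(Z2,Z3) = −0.5 × r = −0.08

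With w = 1/6 they are 0.30, 0.42 and −0.05.

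**Step 3: power through the sequence 1-2-3.** Independence gives 0.8² = 64% and 0.8³ = 51%. The other rows come from trivariate normal simulation (4 million draws, critical value 1.96).

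| Joint effects | Outcome 1 | Outcome 2 | Outcome 3 |
|---|---|---|---|
| Each test at 80% alone, independent | 80% | 64% | 51% |
| Each test at 80% alone, correlated | 80% | 67% | 56% |
| Outcome 1 as age-weighted mix | 95-97% | 75-78% | 61-65% |
| 18% and 23% on outcomes 1 and 2, outcome 3 at its 80% effect | over 99% | 91% | 73% |

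For the third row, outcome 1's effect is w × (outcome 2 effect) + (1 − w) × (outcome 3 effect). With 8.55 and 2.64 this is 3.48 (w = 1/7) or 3.63 (w = 1/6); with 8.8 and 2.7 it is 3.57 or 3.72. That is about 13-14% of 27. It assumes that infants gain equally in both active arms and that azithro 1-11 has no effect at 12-59 months. For the fourth row, 18% of 27 = 4.86 and 23% of 45 = 10.35, both percentages from protocol section 2.

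**Step 4: no effect of infant-only treatment.** Take outcomes 1 and 3 at 80% alone. Outcome 3 is declared about 1.8-1.9% of the time if only a favourable outcome 2 opens the gate, and about 3.1% if a two-sided rejection in either direction does. With outcome 1 near certain, these become about 1.9% and 4.0%. Neither can exceed outcome 2's 5% error rate.

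**Step 5: the claim about power.** With each test at 80% alone, Holm across all three outcomes gives about 74%, 75% and 75%, against 80%, 67% and 56% for the sequence. The sequence gains on outcome 1 and loses on the other two.

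**The case against.** The strongest reply is that 67% and 56% describe an unlikely joint scenario. The outcomes are linked: outcome 1's effect is roughly the age-weighted mix of the other two. For outcome 1 to be only 2.7 while outcome 3 is 2.64, infants in the azithro 1-59 arm may gain only (2.7 − (6/7)·2.64)/(1/7) = 3.06 per 1,000, while infants in the azithro 1-11 arm gain 8.55. That runs opposite to a herd effect. This point stands, and it is why 75-78% and 61-65% belong beside the lower figures. It does not restore 80%.

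A reader might infer that outcome 3 is blocked exactly where it matters most. That is arguable. If infant-only treatment fails against placebo while azithro 1-59 succeeds, the choice of strategy is largely made already. The 2-3% is essentially outcome 2's false-positive rate, and the lower end needs a directional gate that the SAP does not state.

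A reader might also infer that nothing justifies the second gate, or that Holm should replace it. The documents do not support either. The list in 3.3.1 is missing from the available text, so its content is unknown. The SAP's revision history (version 4, July 2020) records the fixed sequence as a deliberate replacement of Bonferroni-Holm. Both control familywise error, and choosing between them ranks the claims. Nor does Holm after outcome 1 deliver 80%: with each test at 80% alone it gives about 65% for outcome 2 and 66% for outcome 3.

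**Conclusion.** The concern holds as a reporting gap. The 80% figures for outcomes 2 and 3 are correct only for tests done alone, and the SAP nowhere gives power through the sequence it prescribes. Outcome 3 is below 80% under every set of effects tried: 51-56% with each test at 80% alone, 61-65% under consistent planning effects, and about 73% with the larger cited effects. Outcome 2 is 64-67%, 75-78% and 91% in the same cases. If infant-only treatment does nothing, outcome 3 is declared about 2-3% of the time.

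These figures rest on the inferred order 1-2-3, correlations derived from the SAP's own SDs and rates, and 1,116 communities in each arm. The protocol's 3,000 communities, if split equally, would give 1,000 per arm and about 60% and 50% at the SAP's absolute effects.

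Error control is sound, and the confidence intervals are reported regardless, although they do not support a confirmatory claim. It would be too strong to conclude that the sequence is invalid, or that 56% is the one true power of outcome 3.

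**What to change.** 1. In SAP 3.2.3, label the 80% figures for outcomes 2 and 3 as power if tested alone.
2. Beside them, give fixed-sequence power under stated joint effects and correlations. At least three cases are needed: each test at 80% alone, outcome 1 as the age-weighted mix, and no effect of infant-only treatment. State whether a significant result in the unfavourable direction opens the next gate.
3. In SAP 3.3.1, qualify the statement about maximizing power: it holds for outcome 1, not for outcomes 2 and 3.

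Leave the testing procedure unchanged. Replacing the second gate with Holm is a trade-off between claims, and it should not be made once arm-level mortality data have been unmasked. SAP section 2 says that an unmasked analysis team was designated in January 2022, and the current SAP version dates from September 2024.

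The cost is wording and a short simulation. The downside is that the stated power becomes less favourable.

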### ***Mortality secondary outcomes***

*Secondary outcome 1:* mortality rate among 12-59 months comparing the 1-11 and Placebo arms. The calculation is similar to *Primary outcome 3*. So assuming a standard deviation of approximately 0.022, we find that 1,116 communities per arm will provide approximately 80% power to detect a 11% relative reduction, assuming a baseline mortality rate of 24 per thousand person-years and an alpha of 0.05. This corresponds to an absolute reduction of 2.7 in the death rate per 1000 person-years.

*Secondary outcome 2:* mortality rate among 1-11 months comparing the 1-11 month and 1-59 month arms. The calculation is similar to *Primary outcome 2*. So assuming a standard deviation of approximately 0.074, we find that 1,116 communities per arm will provide approximately 80% power to detect a 19% relative reduction, assuming a baseline mortality rate of 45 per thousand person-years and an alpha of 0.05. This corresponds to an absolute reduction of 8.8 in the death rate per 1000 person-years.

Sensitivity analyses for secondary outcomes based on reduced enrollment caused by security or logistical concerns: With 791 communities per arm, we anticipate the following relative detectable effect sizes (respectively): 13% and 23%, for 12-59 month olds and 1-11 month olds.

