## 3.2. Study Methods

### 3.2.1. Trial design

AVENIR is designed as a large simple double-masked cluster-randomized trial with response-adaptive allocation (a platform, perpetual trial). The rationale for adaptive randomization is to allow all communities to have the opportunity to be treated, and to allow the program to evolve into the optimal treatment. If new treatment arms are added to AVENIR in the future, or if any of the current treatment arms are discontinued, the Protocol and SAP will reflect those updates.

Eligible communities in Niger will be randomly selected to participate in a mortality/resistance trial, a delivery trial or a delayed intervention.

In the mortality/resistance trial, communities will be randomized to one of three azithromycin distribution strategies: 1) **azithro 1-11**: biannual oral azithromycin to children 1-11 months old with biannual oral placebo to children 12-59 months old, 2) **azithro 1-59**: biannual oral azithromycin to children 1-59 months old, or 3) **placebo**: biannual oral placebo to children 1-59 months old. Mortality will be monitored through biannual census data collection, which will be used to adaptively allocate treatment assignments after the first year. Communities will keep their group assignment for 4 distributions. Antimicrobial resistance will be monitored in a random subsample of treated and untreated children and adults in the Dosso region. See Figure 1 for a summary of the design.

Details are provided in the Protocol document, INV\_002454\_2019.

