### **Mortality/Resistance Trial Interventions**

Communities will be randomized to the following 3 arms, with the allocation updated after a run-in period of 1 year according to the effect of each on the mortality rate among children aged 1-59 months as determined by inter-census intervals:

- Azithromycin 1-11: biannual weight- or height-based dose of oral azithromycin suspension to children 1-11 months old and oral placebo to children 12-59 months old
- Azithromycin 1-59: biannual weight- or height-based dose of oral azithromycin suspension to children 1-59 months old
- Placebo: biannual weight- or height-based dose of oral placebo to children 1-59 months old

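### Mortality secondary outcome 2 is sized on primary outcome 2's baseline of 45 per 1,000 although infants are treated in both arms, so 19% and 8.8 per 1,000 cannot both stand if treating infants works

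*SAP*

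**What the plan says.** SAP 3.2.3 (Mortality secondary outcomes) describes secondary outcome 2 as "mortality rate among 1-11 months comparing the 1-11 month and 1-59 month arms". It says the calculation resembles that for primary outcome 2 and repeats its inputs: SD 0.074, 1,116 communities per arm, alpha 0.05, and approximately "80% power to detect a 19% relative reduction, assuming a baseline mortality rate of 45 per thousand person-years", equated to 8.8 per 1,000 person-years. For reduced enrolment (791 communities per arm) it gives detectable reductions of "13% and 23%, for 12-59 month olds and 1-11 month olds".

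Primary outcome 2 compares the azithro 1-11 arm with placebo and takes as its baseline a "mortality rate of 45 deaths per thousand person-years among children 1-11 months old".

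On what infants receive, SAP 3.2.1 gives the azithro 1-11 arm as "biannual oral azithromycin to children 1-11 months old with biannual oral placebo to children 12-59 months old". The azithro 1-59 arm is "biannual weight- or height-based dose of oral azithromycin suspension to children 1-59 months old" (Mortality/Resistance Trial Interventions).

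**The concern.** Infants in the azithro 1-11 arm play two parts. In primary outcome 2 they are the treated group, expected to fall 8.8 per 1,000 below a baseline of 45. In secondary outcome 2 they are the reference group, and there the SAP gives them the full 45. Both can hold only if azithromycin does nothing for infants when only infants are treated.

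The comparison matters because it tests whether also treating children aged 12-59 months protects infants further. The Protocol's Background and Rationale raises that herd effect, and it bears on the first objective in SAP 3.1.2, the best age group to treat. A null result set against a stated 80% power for a 19% reduction could be taken as firmer evidence of no added benefit than the design can give.

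Secondary outcome 1 reuses the primary outcome 3 inputs in the same way but does not share the fault: children aged 12-59 months in the azithro 1-11 arm receive placebo, so its reference group is untreated.

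**Working it through.** **Inputs (SAP 3.2.3 and 3.2.4).** n = 1,116 communities per arm, SD = 0.074 (74 per 1,000), baseline 45 per 1,000, two-sided alpha 0.05, Z-test on community rates with one common SD and equal arms.

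**Formulas.** SE = SD × √(2/n). Detectable difference at 80% power = (1.960 + 0.842) × SE. Power for a difference d = Φ(d/SE - 1.960).

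**1. Reproduce the plan's figure.**
- SE = 74 × √(2/1,116) = 3.13 per 1,000.
- Detectable difference = 2.802 × 3.13 = 8.78 per 1,000, which is 19.5% of 45.
- Power for d = 8.8 is 80.2%. Power for exactly 19% of 45 (d = 8.55) is 77.9%, so the stated 19% is 19.5% rounded down.
- With 791 per arm: SE = 3.72, detectable difference 10.42, which is 23.2% of 45.

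The SAP's figures follow from its inputs. The formula is not in question; the reference rate is.

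**2. Reference rate for treated infants.** Under the effect primary outcome 2 is sized for, it is 45 - 8.8 = 36.2 per 1,000. A further 19% reduction is 0.19 × 36.2 = 6.88 per 1,000.

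**3. Repeat the calculation at 36.2.** The SAP gives no SD for treated communities, so three cases are shown. The square-root and proportional cases are assumptions.

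| SD assumption | SD | SE per 1,000 | Power for 19% | Detectable difference per 1,000 | As % of 36.2 | At 791 per arm |
|---|---|---|---|---|---|---|
| Fixed, as in the SAP | 0.0740 | 3.13 | 59% | 8.78 | 24.2% | 28.8% |
| Square root of rate: 0.074 × √(36.2/45) | 0.0664 | 2.81 | 69% | 7.87 | 21.7% | 25.8% |
| Proportional: 0.074 × 36.2/45 | 0.0595 | 2.52 | 78% | 7.06 | 19.5% | 23.2% |

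**4. Check the stated pair.** 8.8/45 = 19.6%, but 8.8/36.2 = 24.3%. With the SD fixed, 8.8 keeps its 80% power but is no longer 19%. With proportional scaling, 19% survives but the absolute difference becomes about 7.1. Square-root scaling changes both. No case keeps 19% and 8.8 together.

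**5. Sensitivity to the reference rate.** Taking 19% off 45, rather than 8.8, gives 36.45 and nearly the same answers: 24.1% detectable and 60% power (fixed SD), or 21.7% and 69% (square root). A smaller infant effect of 10% (reference 40.5) gives 21.7% and 69% (fixed), or 20.6% and 73.5% (square root). With no infant effect the reference stays at 45 and the SAP's figures stand.

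**The case against.** **The SD would probably fall too.** This largely stands, and it is why the result is a range. The SAP's own inputs look close to count noise. Rate divided by SD squared gives implied person-years per community of 0.045/0.074² = 8.2 at 1-11 months and 0.024/0.022² = 49.6 at 12-59 months. Their ratio of 6.0 is near the roughly five older children per infant reported in the Protocol's Background. That is indicative, not proof, but it favours square-root scaling. A reader might infer flatly that power is 59% and only a 24% reduction is detectable; those figures belong to the least favourable SD case.

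**The baseline is not labelled as a placebo rate.** True. SAP 3.2.3 says only that rates and SDs were informed by MORDOR Niger and names no arm. That 45 is the placebo rate is inferred from its role in primary outcome 2. The shortfall also depends on infant-only treatment lowering mortality, which primary outcome 2 tests.

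**The absolute difference is still covered.** True with SD 0.074. But the parameter of interest in SAP 3.5.2 is the incidence rate ratio, so the percentage matters.

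**MORDOR's infant reduction of about 23%.** A reader might apply it to 45 and get a still lower reference rate and a larger shortfall. The documents do not support that. The 23% came from treating all children aged 1-59 months, and the Protocol says herd protection may have contributed to it and that treating 1-11 months alone is untested. It approximates the azithro 1-59 arm, not the reference arm here.

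**The consequence is small.** Mostly right. This outcome did not size the trial, 95% confidence intervals are reported whatever the tests show (SAP 3.3.1), and primary outcome 3 bears more directly on the choice of age group. Nothing here implies that the trial needs more communities.

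**Conclusion.** The statement is wrong as written, with limited consequence. If treating infants alone has the effect primary outcome 2 is sized for, the reference rate is about 36.2 per 1,000. With 1,116 communities per arm, 80% power then applies to a reduction of about 22% to 24%, and power for 19% is about 69% to 59%. With 791 per arm the detectable reduction is about 26% to 29%, not 23%. The first figure of each range assumes that the SD scales with the square root of the rate; the second keeps it at 0.074. If the SD fell in full proportion to the rate, 19% would survive but 8.8 would become about 7.1, so the stated pair fails under every SD assumption unless infant treatment has no effect.

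The result rests on reading 45 as the untreated rate, on the SAP's equal split of 1,116 per arm, and on its Z-test. The Protocol gives 3,000 communities with adaptive allocation; an equal 1,000 per arm would give about 23.0% (square-root SD) to 25.6% (fixed SD).

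**What to change.** In SAP 3.2.3, secondary outcome 2:

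- State a reference rate for azithromycin-treated infants (36.2 per 1,000 under the primary outcome 2 assumption) and the SD assumption used with it.
- Restate the detectable relative reduction as a range: about 22-24% with 1,116 communities per arm and about 26-29% with 791 per arm, each with the absolute difference that matches it.
- Remove the sentence likening the calculation to that for primary outcome 2.

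The cost is a few lines of SAP text and a rerun of the existing power notebook. The stated figure becomes less favourable. Enrolment, conduct and analysis are unaffected.
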